Pre-NDPP: A theory-driven, pragmatic solution to improve NDPP effectiveness. Implementing a "pre-session" prior to NDPP enrollment (Pre-NDPP) may be a pragmatic strategy for delivering a theory-driven educational and motivational intervention to bolster the NDPP's effectiveness. Pre-sessions have been recommended to increase NDPP engagement,³⁴ without supporting evidence prior to our recently published pilot study.³⁵ In brief, we developed and pilot-tested a novel strategy to improve attendance and weight loss in the NDPP in which diverse and predominately underserved participants attended a pre-session that provided 1) education about diabetes risks, 2) brief MI to participate in the NDPP, and 3) problem-solving of barriers to participation, based on well-known findings that sufficient engagement in the NDPP generally yields good weight loss^{4,22}. Our pre-session strategy pilot study was highly successful (see Preliminary Data below) but results require confirmation from an adequately powered randomized trial to justify dissemination efforts.

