Research gap and scientific rationale of proposed study. NDPP outcomes are suboptimal, especially for disadvantaged populations, which risks further widening of health disparities if not addressed. Pilot data show feasibility and promising results of Pre-NDPP among diverse, underserved patients with elevated diabetes risks, but are limited by small sample size of the intervention group and no concurrently randomized control group. To address the research gap, we propose a randomized controlled trial (RCT) to compare NDPP attendance and weight loss among diverse, predominately underserved participants who receive Pre-NDPP vs. direct enrollment into NDPP (usual care). The primary hypothesis generated by pilot data and above-cited literature is that pre-sessions improve NDPP engagement and weight loss, which will be confirmed if those randomized to Pre-NDPP have better outcomes than those receiving usual care NDPP. A secondary analysis will examine whether only Pre-NDPP participants who go on to NDPP benefit (vs. no benefit for those declining NDPP), which would suggest that pre-sessions screen for individuals likely to participate adequately, and thus benefit from, the NDPP. Screening via pre-sessions may yet be an efficient population health strategy to a) increase risk awareness for the estimated one-third of US adults with prediabetes, 1 b) offer informed decisionmaking, and c) maximize performance-based reimbursement for suppliers, which supports access³⁶. In either case, a brief group model may be optimal as: 1) Individual pre-sessions appear cost-prohibitive, while longer sessions may also be more taxing on vulnerable populations; 2) Uptake by NDPP suppliers likely depends on establishing efficacy in a low-cost, high-reach model; 3) A key goal is supporting engagement in the yearlong NDPP for continued intervention, and thus increasing familiarity with its hour-long, group class format may be important (held remotely and/or in-person as allowable in the era of COVID-19). If effective, greater uptake is expected if NDPP providers and payers can understand how Pre-NDPP achieves an effect and whether their populations are likely to benefit, which will be addressed via mediation and moderation analyses. To prepare for future dissemination, we will also evaluate implementation factors, including cost of adding pre-sessions to NDPP delivery and estimated return on investment (ROI). If effective, this approach may reduce disparities in NDPP effectiveness. It can also be disseminated to all NDPP providers, including more than 1,700 suppliers⁹, and may be supported by current NDPP payers such as Medicare, commercial insurers, and employer groups. 10-12 Thus, Pre-NDPP has potential for high impact on the burden of T2D and related health disparities across the country.

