We will measure Pre-NDPP costs using principles of time-driven activity based costing, ^{48,49} accounting for Lifestyle Coach and supervisor time (including salaries and benefits), supplies and other direct costs, and indirect costs (e.g., facilities and general administrative expenses). To focus on Pre-NDPP, we will exclude other costs associated with standard NDPP delivery and research-related costs (e.g., data collection solely for research purposes). To facilitate accurate estimates of personnel costs, coaches and their supervisor will track time spent on Pre-NDPP activities (e.g., training, outreach, preparing for and conducting Pre-NDPP) and report total hours for each Pre-NDPP activity quarterly. Supplies and other direct costs will also be reported quarterly. Standard cost collection guides will be used by study staff.

| Measure | easure Description Method of Collection | | | | | |
|--|--|--|---|--|--|--|
| Characteristics | | | | | | |
| Demographics | Age, gender, race/ethnicity, primary language, income, education, household composition, etc | Collected from EHR and during first study visit | BL | | | |
| Body mass index | Baseline body mass index (kg/m²) | Collected during first study visit (or within 1-2 weeks of remotely-conducted initial study visits) | | | | |
| | Main outcom | les | T | | | |
| Initial NDPP attendance | ≥1 NDPP session attended 1-25 NDPP sessions attended | Collected during NDPP delivery; | | | | |
| # of sessions attended | (including virtual vs. in-person sessions) | Note weight is also measured at an initial study assessment and at a final 12-month study visit | | | | |
| Duration in NDPP | 1-365 days of NDPP participation | (we are setting up a time for all randomized individuals to have | | | | |
| # of between-session calls completed | 1-25 between-session support calls completed | their weight measured at these study visits, for which they will | Ongoing collection | | | |
| Physical activity | Average self-reported weekly minutes at each NDPP session | receive gift cards). Participants may also text/email a picture of | | | | |
| Percent weight change | Based on a) BL to 12 months (primary outcome), and b) first to last NDPP sessions attended | their weight using a study- provided scale for in-home use if not meeting in-person for weight | | | | |
| ≥5% weight loss | Achieved at any point in the NDPP | collection. | | | | |
| | Mediators | | T | | | |

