Coaches will then use MI techniques (e.g., reflective listening, evoking ambivalence, rolling with resistance, and eliciting change talk)²⁹ to help participants identify their preferred plan of action to reduce risk, encouraging participation in NDPP sessions. For example, to create discrepancy, coaches will acknowledge the difficulty of making changes in health behavior and probe for typical experiences of weight loss followed by weight regain or other similar challenges. To counter-balance these challenges, coaches will encourage participants to describe why preventing T2D is important to them (e.g., wanting to live a long and healthful life or setting a positive example for their children and grandchildren). Coaches will also non-judgmentally acknowledge that while the NDPP works well for those who attend regularly, it may be challenging for some individuals to attend a yearlong class, and that it is okay to opt out or choose other risk reduction resources.

Finally, to plan behavior to reduce diabetes risk, participants will be guided toward developing a personalized SMART (Specific, Measurable, Achievable, Realistic, and Time-bound) strategy for attending the NDPP. Coaches will help participants identify their anticipated barriers to attendance (e.g., need for childcare) and possible solutions that would enable participation (e.g., finding other caregivers or bringing children to class on occasion if needed). Participants will also be encouraged that more frequent attendance is associated with greater weight loss, but overall benefits can be achieved despite missing some sessions: attending ≥15 sessions is associated with achieving the ≥5% weight loss goal on average (i.e., each session is associated with 0.31% weight loss⁴). Scaling questions will be used to help individuals identify an appropriate initial goal. For example, although some participants may have limited confidence to make a commitment to attend the yearlong NDPP without having tried it before, they may report a 10 of 10 in confidence to attend at least the first NDPP session. Lastly, participants will complete an individualized action plan that includes their SMART goal and anticipated problem-solving strategies.

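### The planned screening analysis splits the Pre-NDPP arm on NDPP uptake after randomization, and the pattern it looks for does not distinguish screening from a real effect or from no effect

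*Combined protocol and SAP*

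**What the plan says.** Section II (Research gap and scientific rationale) first ties the main hypothesis to the randomized comparison, "which will be confirmed if those randomized to Pre-NDPP have better outcomes than those receiving usual care NDPP". It then adds a secondary analysis of whether benefit is confined to those in the Pre-NDPP arm who go on to NDPP, and gives that pattern a meaning: "vs. no benefit for those declining NDPP), which would suggest that pre-sessions screen for individuals likely to participate adequately". The text goes on to describe screening as a possibly efficient population-health strategy, partly because it would help suppliers under performance-based payment.

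Two other places bear on this. Section II (Pre-NDPP: A theory-driven, pragmatic solution) says the pre-session strategy is "based on well-known findings that sufficient engagement in the NDPP generally yields good weight loss". Section IV.C (Description of the Pre-NDPP protocol) has coaches encourage NDPP participation but also tell participants "that it is okay to opt out or choose other risk reduction resources".

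The Data Analysis Plan (Section IV.F) does not mention the screening analysis. It gives no comparator, model, causal assumptions or selection caveat for it. It does plan ITT percent weight change in all randomized participants (Hypothesis 1.1) and attendance of at least one NDPP session by arm (Hypothesis 1.2), but links neither to the screening question.

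**The concern.** Whether pre-sessions improve outcomes or only filter out people who would have done poorly is a question the trial needs to answer. The pilot could not: it compared 75 people who took a pre-session and then enrolled with earlier participants, and collected nothing further on the 15 who took a pre-session and did not enroll.

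The proposed rule divides one arm by a choice made after randomization. Those who go on are self-selected, and the session they have just attended was designed to affect that choice. Decliners receive no NDPP, so if the effect runs through NDPP they should show no benefit under either explanation. Followed as written, the plan could report a mechanism, with a service recommendation attached, from a pattern that would have appeared anyway.

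**Working it through.** **The plan's own figures.** None is given for this analysis. The only power figures are in Table 2, for the primary outcome, and all six rows reproduce. For example, effective n = 10 × 20 / (1 + 19 × 0.01) = 168.1 per arm (stated 168), and power at effect size .31 is 81.1% (stated 81%). Table 2 is not in question.

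**Inputs**
- Decliners: 20% of the Pre-NDPP arm. This borrows the expected early attrition in Section IV.C (Recruitment); the pilot figure was 15/90 = 17%.
- Weight loss: 3.4% with a pre-session and 1.5% without (Section III, Results).
- SD: (3.4 − 1.5) / 0.36 = 5.3, using the pilot effect size.
- Assumed: Pre-NDPP participants who start NDPP (starters) lose 3.4% and decliners lose 0.

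**Three explanations giving the same Pre-NDPP arm**
- A, screening only: the 20% who decline would have lost 0 anyway. In usual care an assumed 70% of such people attend at least once, so uptake there is 0.80 + 0.20 × 0.70 = 94%.
- B, pre-sessions work through NDPP: usual-care uptake is also 80%, and starters there lose 1.5%.
- C, no effect and no screening: usual-care uptake is 80%, and starters there lose 3.4%.

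The Pre-NDPP mean is 0.80 × 3.4 = 2.72 throughout. The usual-care mean is 0.80 × 3.4 = 2.72 in A and C, and 0.80 × 1.5 = 1.20 in B.

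| Contrast (percentage points) | A screens | B works | C neither |
|---|---|---|---|
| Starters − decliners, within Pre-NDPP | 3.40 | 3.40 | 3.40 |
| Starters − all usual care | 0.68 | 2.20 | 0.68 |
| Decliners − all usual care | −2.72 | −1.20 | −2.72 |
| ITT difference | 0 | 1.52 | 0 |
| Uptake, Pre-NDPP vs usual care | 80% vs 94% | 80% vs 80% | 80% vs 80% |

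A simulation with 1,000,000 per arm agreed to within 0.04 points.

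**Reading the table.** The first row uses no usual-care data, so it carries no information on what the pre-session caused. Against all usual care, starters look better and decliners worse in every column. The sizes differ in B only because usual care as a whole did worse, which the ITT row already shows.

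A third comparator would be starters against usual-care starters. That gives 3.4 − 2.72/0.94 = 0.51 in A, 3.4 − 1.5 = 1.90 in B and 0 in C, with decliners at 0 against usual-care decliners throughout. It removes C, but A and B, the two that need separating, still share the pattern of benefit only in starters.

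**Sensitivity.** With 17%, 30% or 50% decliners the within-arm contrast stays at 3.4 in every scenario (3.38 to 3.43 simulated). The ITT difference in B is 0.83 × 1.9 = 1.58, 0.70 × 1.9 = 1.33 and 0.50 × 1.9 = 0.95, and remains 0 in A and C.

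**Chance of finding the pattern.** With 250 per arm, 20% decliners gives 200 starters and 50 decliners. SE = 5.3 × √(1/200 + 1/50) = 0.84, and 3.4/0.84 = 4.06. Power is about 98%, even in C. This ignores clustering and missing 12-month weights.

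**The case against.** The best defence is that the decliner question has content. The pre-session is itself an intervention, with risk education, motivational interviewing, other resources and an action plan, and Section II says that awareness of risk may by itself change behaviour. Twelve-month weights are sought from everyone randomized, so decliners will have outcomes, unlike in the pilot. This stands in part. A direct effect on decliners is possible, so it would go too far to infer that their result carries no information whatever the mechanism. But detecting such an effect needs the usual-care participants who would have declined after a pre-session, and the plan defines no such group.

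The wording is also modest. The analysis is secondary, sits in the background section and says only that the pattern would suggest screening. The preceding sentence rests the main hypothesis on the randomized comparison. All of this limits the consequences without making the inference sound.

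Two stronger readings are tempting and unsupported. A reader might infer a bias of known size and direction in favour of Pre-NDPP starters over usual-care starters. The plan does not describe that comparison or give expected uptake by arm, and the direction would reverse if uptake were higher in Pre-NDPP. A reader might also infer from "1-25 NDPP sessions attended" in Table 1 that never-attenders drop out of the analysis. That is a descriptive range. The adjacent row records whether any session was attended, and Section IV.F includes all randomized participants in ITT analyses regardless of participation.

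**Conclusion.** The point holds for the secondary screening inference. Benefit confined to starters, with none in decliners, is expected if pre-sessions work through attendance, if they only screen, and, when judged within the arm or against all usual care, if they do nothing. In the illustration the within-arm contrast is 3.4 points in all three cases; the ITT difference (1.52 vs 0) and uptake by arm (80% vs 94%, or equal) are what separate them.

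The SD, decliner share, scenario means and the 70% figure are assumptions. The failure to discriminate does not depend on their values, but it does rest on the effect running mainly through NDPP, as the protocol proposes. Nothing here touches the primary ITT test, its power or the sample size, and a reader should not infer that the main result is biased.

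**What to change.** In Section II and the Data Analysis Plan, base the efficacy-versus-screening interpretation on the two randomized contrasts already planned: the ITT difference in 12-month percent weight change, and the proportion attending at least one NDPP session by arm. State in advance:

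- A positive ITT difference supports a real effect.
- A near-nil ITT difference with lower uptake in Pre-NDPP is compatible with screening.
- A near-nil ITT difference with equal uptake supports neither.

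Near-nil should be judged by the confidence interval, not by a non-significant test. With SD 5.3 and 168 effective participants per arm, the 95% half-width is 1.96 × 5.3 × √(2/168) = 1.1 points, so an estimate of zero would still leave moderate effects open.

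Report any starter/decliner split as descriptive only, with its comparator named and a caveat that the groups are self-selected after randomization.

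The cost is a change of wording and a more modest screening conclusion. No new data or models are needed.

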Data collection for Aims 1 and 2. This RCT focuses on comparing NDPP outcomes between participants who receive Pre-NDPP vs. direct enrollment into the NDPP. The assessment schedule is shown in Table 1 below. Demographic characteristics will be extracted from EHR databases and verified as needed during the first study visit, including age, gender, race/ethnicity, preferred language, income (above/below 133% of federal poverty level), and education (highest level completed). Body weight will be measured on a high-capacity medical-quality scale at study visits and NDPP sessions. We will also provide study participants with a commercial-grade scale for in-home use (e.g., Inevifit's Premium Bathroom Scale I-BS002; https://www.inevifit.com/product/inevifit-premium-bathroom-scale-w-led-display-silver/) so that they can send us a picture of their weight via text message or email when not meeting in-person. The primary outcome is percent weight change from baseline to 12-months by ITT analysis (without regard to whether participants declined NDPP or had early dropout). We will also calculate percent weight change from the first to last NDPP sessions attended (i.e., last observation carried forward), per CDC guidelines.³⁷ CMS standards for NDPP reimbursement also emphasize achieving ≥5% weight loss at any point in the program, ¹⁰ assessed as a

dichotomous outcome. Attendance in the NDPP will be measured as ≥1 session attended, total number of NDPP sessions attended (including make-up sessions), and duration of participation in the yearlong program. We will also record how many sessions were attended remotely vs. in-person. Rates of completing between-session support calls will also be assessed as an additional indicator of engagement and treatment dose. Per the CDC's NDPP curriculum, participants will self-report weekly minutes of moderate to vigorous physical activity since the last session.³ Baseline BMI will also be assessed at the initial study visit as kg/m². If the initial study visit is held remotely (i.e., due to restrictions to meeting in-person per COVID-19), we will collect BMI by confirming height from a participant's medical record, and mailing a scale to participants for them to send us a picture of their weight within 1-2 weeks.

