General quantitative approaches. Differences in characteristics between study groups will be assessed using chi-square and t-tests to examine potential sampling bias. Percent weight change is the primary outcome, which has a well-documented association with T2D incidence.^{2,20} ITT analyses will include all randomized participants regardless of NDPP participation, including those lost to follow up. Weight loss data for women who become pregnant during the study will be excluded from analyses. Patient-level covariates will be screened in bivariate analyses and included in multivariate analysis if related to the outcome at p<.2, differ between treatment arms, or associated with dropout. Covariates and potential moderators will include age, gender, race/ethnicity, primary language, comorbidities, and other demographic and clinical variables. Although primary analyses examine a single outcome per patient (e.g., percent weight loss), for longitudinal analyses (e.g., perceived risk) we will determine whether missingness patterns are ignorable or nonignorable. 51-54 If so, we will employ likelihood-based methods that use all available data, adjusting for covariates associated with missingness. If missingness is non-ignorable we will use pattern mixture models.⁵⁵ If normality assumptions are not met, we will use transformations to normalize distributions, ordinal or Poisson regression where appropriate, and/or the appropriate link function and distribution (e.g., logit link, gamma distribution). We will use general (generalized) linear mixed models to incorporate data structures that may be both hierarchical (patients within groups) and longitudinal (repeated observations over time). 56,57 Hypothesis tests will be two-sided with α=.05 or p values reported. Goodness of fit statistics and model fitting diagnostics will be used to assess for influential points, outliers, overdispersion, and heteroscedasticity and to evaluate alternative model specifications.⁵⁷ SAS version 9.4 (SAS Institute Inc., Cary, NC) will be used for analyses.

Aim 1: To evaluate clinical effectiveness of the Pre-NDPP intervention.

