Hypothesis 1.1. Pre-NDPP participants will experience greater weight loss than those directly enrolled into NDPP. The primary outcome for this analysis will be percent weight change among all randomized participants. As study participation includes groups of individuals in the same study arm, the data structure will be hierarchical, with patients nested within groups. Statistical models are shown in hierarchical notation below.

Likelihood of achieving ≥5% weight loss in the NDPP will also be evaluated (using generalized linear mixed models with logit link), as well as percent weight change from first to last NDPP sessions attended.

Level 1 model. Individual outcomes will be modeled as a function of patient characteristics (fixed effects), such as sociodemographic variables, baseline BMI, and comorbid conditions: $Y_{ij} = \beta_{0j} + \beta_{1j} X_{1ij} + \beta_{2j} X_{2ij} + ... + \beta_{pj} X_{pij}$ Level 2 model. Group level models specify relationships between group-level predictors and coefficients in the Level 1 model. The intervention effect is included as 0 if control, 1 if intervention: $\beta_{0j} = \gamma_{00} + \gamma_{01}$ (intervention)+ u_{0j} . Thus, for a standardized model, γ_{00} is adjusted mean weight loss for patients in the standard condition (i.e., no pre-session intervention), γ_{01} represents the average increment (decrement) from the mean for groups with intervention patients, and u_{0j} is a group level random effect that reflects between-group variance and is the difference between group means and the predicted mean based on the model, and $u_{0j} \sim N(0,\tau_{00})$. Thus, Hypothesis 1.1 can be tested as H_0 : γ_{01} =0 vs H_1 : γ_{01} ≠0.

Hypothesis 1.2. Pre-NDPP participants will have greater engagement in the NDPP than those who are directly enrolled into the program. The outcome variables, number of sessions attended and days of participation, will be analyzed using similar approaches. If the distribution of outcomes is non-normal we will use generalized linear mixed models with the appropriate distribution and link function, as described above. We will also examine the dichotomous outcome of ≥1 NDPP session attended using multilevel logistic regression (generalized linear mixed model with logit link and random effect for group).

Aim 2: To examine mediators and moderators of Pre-NDPP outcomes.

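### Table 1 starts the session and duration scales at 1, so randomized participants who never attend NDPP have no value on two Hypothesis 1.2 outcomes

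*Combined protocol and SAP*

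**What the plan says.** Table 1 (IV.A, Main outcomes) gives three engagement measures a range: "1-25 NDPP sessions attended", "1-365 days of NDPP participation" and "1-25 between-session support calls completed". The text of IV.A sets no lower bound. It says attendance "will be measured as ≥1 session attended, total number of NDPP sessions attended (including make-up sessions), and duration of participation in the yearlong program".

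The Data Analysis Plan (IV.F, General quantitative approaches) states: "ITT analyses will include all randomized participants regardless of NDPP participation, including those lost to follow up". Section I likewise presents the trial as an intent-to-treat test of effects on attendance as well as weight loss.

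Hypothesis 1.1 restates its analysis set: "The primary outcome for this analysis will be percent weight change among all randomized participants". Hypothesis 1.2 does not. It says only: "The outcome variables, number of sessions attended and days of participation, will be analyzed using similar approaches". It adds a separate logistic model for attending at least one session. Support calls are not named there.

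For non-normal outcomes, IV.F allows transformations, Poisson or ordinal regression, or another distribution and link, with gamma given as an example.

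**The concern.** Whether a person starts NDPP is settled after randomization, and the pre-session acts on that decision from both sides. It promotes attendance, and it also tells participants that "it is okay to opt out or choose other risk reduction resources" (IV.C, Description of the Pre-NDPP protocol). Section II allows that pre-sessions may work partly by screening for people likely to take part. If non-starters have no value, the mean sessions and days are compared between two groups that the intervention itself may have selected differently. Such a comparison cannot separate better engagement from a change in who begins.

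The engagement half of the Section II hypothesis is at stake, as are the Aim 2 mediation and moderation models that use session attendance. An analyst who met the gap after seeing the data could resolve it either way.

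**Working it through.** **How many are affected.** IV.C Recruitment gives 500 enrolled and about 20% early attrition. 500 × (1 − 0.20) = 400, which reproduces the plan's goal of 400 attending at least one session. That leaves 500 − 400 = 100 randomized participants with no admissible value on a scale of 1-25 sessions or 1-365 days.

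**Is zero implied?** For sessions it arguably is, since a total over no sessions is 0. Duration is less clear: without a first session there is no start date, so a rule is needed. The model choice also matters. A gamma distribution and a plain log transform both exclude zero, so either would remove non-starters even if the ranges were corrected. Poisson would not.

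**What the choice does to the estimate.** With non-starters scored 0, the mean over all randomized = start rate × mean among starters. The starter means below come from the pilot (Section III): 49.3% v 35.0% of sessions and 196.3 v 96.5 days. I apply the percentages to this trial's 25 sessions: 0.493 × 25 = 12.325 and 0.350 × 25 = 8.75. Start rates by arm are assumptions, chosen so that 80% start overall.

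The starters-only differences are 12.325 − 8.75 = 3.575 sessions and 196.3 − 96.5 = 99.8 days, whatever the start rates. Over all randomized participants (differences taken before rounding):

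| Start rate, Pre-NDPP / usual care | Sessions | Days |
|---|---|---|
| 80% / 80% | 9.86 − 7.00 = 2.86 | 157.0 − 77.2 = 79.8 |
| 85% / 75% | 10.48 − 6.56 = 3.91 | 166.9 − 72.4 = 94.5 |
| 75% / 85% | 9.24 − 7.44 = 1.81 | 147.2 − 82.0 = 65.2 |

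Three further cases for sessions, with usual-care starters averaging 8.75:

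- **Equal means among starters.** The starters-only difference is 0. Over all randomized it is 8.75 × (0.85 − 0.75) = +0.875 if Pre-NDPP has the higher start rate, and −0.875 if the rates are swapped.
- **Pure screening.** 85% start in usual care and 75% in Pre-NDPP, with equal attendance per randomized participant: 0.85 × 8.75 = 7.4375 in both arms. Pre-NDPP starters then average 7.4375 / 0.75 = 9.92. The starters-only difference is 9.92 − 8.75 = +1.17, and the true difference is 0. The false gain is 1.17 / 3.575 = 33% of the pilot difference.
- **Drawing in hesitant people.** 75% start in usual care and 85% in Pre-NDPP, and the added 10% attend 4 sessions each (assumed). Pre-NDPP averages 0.75 × 8.75 + 0.10 × 4 = 6.5625 + 0.40 = 6.9625 per randomized participant, a true gain of 0.40. Starters average 6.9625 / 0.85 = 8.19, so the starters-only difference is 8.19 − 8.75 = −0.56. The sign reverses.

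**The case against.** The strongest reply is that the plan already covers this. The ITT sentence stands under general approaches, and Hypothesis 1.2 follows the approach of Hypothesis 1.1, which is over all randomized participants. The Retention section says dropout does not prevent a test of the effect on attendance, because engagement is itself an outcome. The look at people who go on to NDPP is a separate secondary analysis (Section II). Table 1 is a measurement table, and its row for attending at least one session deals with the zero category. That binary outcome and the Reach measure would also make any screening visible.

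Much of this stands. A reader might infer from Table 1 that Hypothesis 1.2 is planned as an attenders-only analysis and that ITT has been abandoned for engagement. The documents do not support that: no section states such a restriction, and several point the other way. Nor are support calls part of the Hypothesis 1.2 comparison.

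It does not dispose of the point. Both Hypothesis 1.2 scales are printed from 1, so the table contradicts the ITT rule and nothing says which governs. The Retention argument holds for never-starters on sessions and days only if they receive a value. The binary outcome does not repair the two quantitative comparisons. The pilot also compared enrollees only: 15 people (17%) who attended a pre-session did not enroll, and no further data were collected on them (Section III). That precedent could carry over by default.

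**Conclusion.** The ranges are wrong as written for sessions and days, and a scoring rule for non-starters is missing. About 100 of 500 randomized participants are affected if the expected attrition holds. The consequence is conditional: bias arises if the ranges, or a model that excludes zero, are applied literally.

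Its size and direction cannot be fixed from the documents. The figures of +1.17 and −0.56 sessions rest on assumed start rates by arm, on an assumed 4 sessions for added starters, and on applying pilot percentages to 25 sessions, which the pilot is not stated to have offered. They show that a false gain and a reversed sign are both possible, not that either is expected.

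A reader might also infer that the main result or the power is compromised. It is not. Percent weight change has its own all-randomized definition, and Table 2 concerns weight loss only. This is a correction to secondary outcomes, worth making before analysis.

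**What to change.** 1. In Table 1, print 0-25 sessions and 0-365 days, and state that a randomized participant who attends no session scores 0 on both.
2. In Hypothesis 1.2, state that sessions and days are compared over all randomized participants, with a model that accommodates zeros. Rule out gamma and a plain log transform for these two outcomes.
3. Report means among attenders as descriptive only.
4. Print support calls as 0-25, using the calls actually recorded. Do not set them to 0 for non-attenders: coaches' calls also serve as reminders of coming sessions (IV.C), so a non-attender may have completed some.

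The cost is a few lines of text. No new data are needed, because attendance is already collected. Reported mean sessions and days will be lower than attender-only means.
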